Arthritis See also Arthralgia	Stiffness or joint swelling causing no or minimal interference with usual social & functional activities	Stiffness or joint swelling causing greater than minimal interference with usual social & functional activities	Stiffness or joint swelling causing inability to perform usual social & functional activities	Disabling joint stiffness or swelling causing inability to perform basic self-care functions
Bone Mineral Loss Pediatric < 21 Years	BMD t-score or z-score -2.5 to -1.0 BMD z-score -2.5 to -1.0	BMD t-score or z-score < -2.5 BMD z-score < -2.5	Pathological fracture (including loss of vertebral height) Pathological fracture (including loss of vertebral height)	Pathologic fracture causing life-threatening consequences Pathologic fracture causing life-threatening consequences
Myalgia (non-injection site)	Muscle pain causing no or minimal interference with usual social & functional activities	Muscle pain causing greater than minimal interference with usual social & functional activities	Muscle pain causing inability to perform usual social & functional activities	Disabling muscle pain causing inability to perform basic self-care functions
Osteonecrosis	NA	Asymptomatic with radiographic findings AND No operative intervention indicated	Symptomatic bone pain with radiographic findings OR Operative intervention indicated	Disabling bone pain with radiographic findings causing inability to perform basic self-care functions

SYSTEMIC				
	Grade 1	Grade 2	Grade 3	Grade 4
Acute Systemic Allergic Reaction	Localized urticaria (wheals) with no medical intervention indicated	Localized urticaria with medical intervention indicated OR Mild angioedema with no medical intervention indicated	Generalized urticaria OR Angioedema with medical intervention indicated OR Symptomatic mild bronchospasm	Acute anaphylaxis OR Life-threatening bronchospasm OR laryngeal edema
Chills	Symptoms causing no or minimal interference with usual social & functional activities	Symptoms causing greater than minimal interference with usual social & functional activities	Symptoms causing inability to perform usual social & functional activities	NA
Fatigue Malaise	Symptoms causing no or minimal interference with usual social & functional activities	Symptoms causing greater than minimal interference with usual social & functional activities	Symptoms causing inability to perform usual social & functional activities	Incapacitating fatigue/malaise symptoms causing inability to perform basic self-care functions
Fever (nonaxillary)	37.7°C to 38.6°C 99.8°F to 101.5°F	38.7°C to 39.3°C 101.6°F to 102.8°F	39.4°C to 40.5°C 102.9°F to 104.9°F	> 40.5°C > 104.9°F
Pain- Indicate Body Site See also Injection Site Pain, Headache, Arthralgia, and Myalgia	Pain causing no or minimal interference with usual social & functional activities	Pain causing greater than minimal interference with usual social & functional activities	Pain causing inability to perform usual social & functional activities	Disabling pain causing inability to perform basic self-care functions OR Hospitalization (other than ER visit) indicated
Unintentional Weight Loss	NA	5% to 9% loss in body weight from baseline	10% to 19% loss in body weight from baseline	≥ 20% loss in body weight from baseline OR Aggressive intervention indicated [eg, tube feeding or total parenteral nutrition]

INJECTION SITE REACTION				
	Grade 1	Grade 2	Grade 3	Grade 4
Injection Site Pain (pain without touching) Or Tenderness (pain when area is touched)	Pain/tenderness causing no or minimal limitation of use of limb	Pain/tenderness limiting use of limb OR Pain/tenderness causing greater than minimal interference with usual social & functional activities	Pain/tenderness causing inability to perform usual social & functional activities	Pain/tenderness causing inability to perform basic self-care function OR Hospitalization (other than ER visit) indicated for management of pain/tenderness
Injection Site Reaction (Localized), > 15 Years Pediatric ≤ 15 Years	Erythema OR Induration of 5 × 5 cm to 9 × 9 cm (or 25–81 × cm ²) Erythema OR Induration OR Edema present but ≤ 2.5 cm diameter	Erythema OR Induration OR Edema > 9 cm any diameter (or > 81 cm ²) Erythema OR Induration OR Edema > 2.5 cm diameter but < 50% surface area of the extremity segment (e.g., upper arm/thigh)	Ulceration OR Secondary infection OR Phlebitis OR Sterile abscess OR Drainage Erythema OR Induration OR Edema involving ≥ 50% surface area of the extremity segment (e.g., upper arm/thigh) OR Ulceration OR Secondary infection OR Phlebitis OR Sterile abscess OR Drainage	Necrosis (involving dermis and deeper tissue) Necrosis (involving dermis and deeper tissue)
Pruritis Associated with Injection See also Skin: Pruritis (itching—no skin lesions)	Itching localized to injection site AND Relieved spontaneously or with < 48 h treatment	Itching beyond the injection site but not generalized OR Itching localized to injection site requiring ≥ 48 h treatment	Generalized itching causing inability to perform usual social & functional activities	NA

ENDOCRINE/METABOLIC				
	Grade 1	Grade 2	Grade 3	Grade 4
Lipodystrophy (e.g., back of neck, breasts, abdomen)	Detectable by study participant or caregiver (for young children and disabled adults)	Detectable on physical exam by health care provider	Disfiguring OR Obvious changes on casual visual inspection	NA
Diabetes Mellitus	NA	New onset without need to initiate medication OR Modification of current meds to regain glucose control	New onset with initiation of indicated med OR Diabetes uncontrolled despite treatment modification	Life-threatening consequences (e.g., ketoacidosis, hyperosmolar non-ketotic coma)
Gynecomastia	Detectable by study participant or caregiver (for young children and disabled adults)	Detectable on physical exam by health care provider	Disfiguring OR Obvious on casual visual inspection	NA
Hyperthyroidism	Asymptomatic	Symptomatic causing greater than minimal interference with usual social & functional activities OR Thyroid suppression therapy indicated	Symptoms causing inability to perform usual social & functional activities OR Uncontrolled despite treatment modification	Life-threatening consequences (e.g., thyroid storm)
Hypothyroidism	Asymptomatic	Symptomatic causing greater than minimal interference with usual social & functional activities OR Thyroid replacement therapy indicated	Symptoms causing inability to perform usual social & functional activities OR Uncontrolled despite treatment modification	Life-threatening consequences (e.g., myxedema coma)
Lipoatrophy (e.g., fat loss from the face, extremities, buttocks)	Detectable by study participant or caregiver (for young children and disabled adults)	Detectable on physical exam by health care provider	Disfiguring OR Obvious on casual visual inspection	NA

GENITOURINARY				
	Grade 1	Grade 2	Grade 3	Grade 4
Intermenstrual Bleeding (IMB)	Spotting observed by participant OR Minimal blood observed during clinical or colposcopic exam	Intermenstrual bleeding not greater in duration or amount than usual menstrual cycle	Intermenstrual bleeding greater in duration or amount than usual menstrual cycle	Hemorrhage with life-threatening hypotension OR Operative intervention indicated
Urinary Tract obstruction (e.g., stone)	NA	Signs or symptoms of urinary tract obstruction without hydronephrosis or renal dysfunction	Signs or symptoms of urinary tract obstruction with hydronephrosis or renal dysfunction	Obstruction causing life-threatening consequences

INFECTION				
	Grade 1	Grade 2	Grade 3	Grade 4
Infection (any other than HIV infection)	Localized, no systemic antibiotal treatment indicated AND Symptoms causing no or minimal interference with usual social & functional activities	Systemic antibiotal treatment indicated OR Symptoms causing greater than minimal interference with usual social & functional activities	Systemic antibiotal treatment indicated AND Symptoms causing inability to perform usual social & functional activities OR Operative intervention (other than simple incision and drainage) indicated	Life-threatening consequences (e.g., septic shock)

Basic Self-care Functions: Activities such as bathing, dressing, toileting, transfer/movement, continence, and feeding.

Usual Social & Functional Activities: Adaptive tasks and desirable activities, such as going to work, shopping, cooking, use of transportation, pursuing a hobby, etc.

Appendix 5. Pregnancy Precautions, Definition for Female of Childbearing Potential, and Contraceptive Requirements

1) Definitions

a) Definition of Childbearing Potential

For the purposes of this study, a female born subject is considered of childbearing potential following the initiation of puberty (Tanner stage 2) until becoming post-menopausal, unless permanently sterile or with medically documented ovarian failure.

Women are considered to be in a postmenopausal state when they are ≥ 54 years of age with cessation of previously occurring menses for ≥ 12 months without an alternative cause. In addition, women of any age with amenorrhea of ≥ 12 months may also be considered postmenopausal if their follicle stimulating hormone (FSH) level is in the postmenopausal range and they are not using hormonal contraception or hormonal replacement therapy.

Permanent sterilization includes hysterectomy, bilateral oophorectomy, or bilateral salpingectomy in a female subject of any age.

b) Definition of Male Fertility

For the purposes of this study, a male born subject is considered of fertile after the initiation of puberty unless permanently sterile by bilateral orchidectomy or medical documentation.

2) Contraception Requirements for Female Subjects

a) Study Drug Effects on Pregnancy and Hormonal Contraception

The data of study drugs on pregnant women is limited or not available. There is no suspicion of human teratogenicity based on class effects or genotoxic potential. Relevant non clinical reproductive toxicity studies for human pregnancy do not indicate a strong suspicion of human teratogenicity/fetotoxicity. Data from clinical pharmacokinetic interaction studies of study drug have demonstrated that there is no reduction in the clinical efficacy of hormonal contraception or that the effect on hormonal contraception is insignificant. Please refer to the latest version of the investigator's brochure for additional information.

b) Contraception Requirements for Female Subjects of Childbearing Potential

The inclusion of female subjects of childbearing potential requires the use of highly effective contraceptive measures. They must also not rely on hormone-containing contraceptives as a form of birth control during the study. They must have a negative serum pregnancy test at Screening prior to study enrollment. A serum pregnancy test will be performed at all study visits and the end of relevant system exposure. In the event of a delayed menstrual period (over one month between menstruations), a serum pregnancy test must be performed to rule out pregnancy. This is even true for women of childbearing potential with infrequent or irregular periods. Female subjects must agree to one of the following from Screening until 30 days following the end of relevant systemic exposure.

- Complete abstinence from intercourse of reproductive potential. Abstinence is an acceptable method of contraception only when it is in line with the subject's preferred and usual lifestyle.

Or

- Consistent and correct use of 1 of the following methods of birth control listed below:
 - Intrauterine device (IUD) with a failure rate of < 1% per year
 - Tubal sterilization
 - Essure micro-insert system (provided confirmation of success 3 months after procedure)
 - Vasectomy in the male partner (provided that the partner is the sole sexual partner and had confirmation of surgical success 3 months after procedure)

Or

- Consistent and correct use of one hormonal method and one barrier method:
 - Barrier methods
 - Diaphragm with spermicide
 - Cervical cap with spermicide
 - Male condom (with or without spermicide)
 - Hormonal methods (the hormonal contraceptive should contain at least 30 mcg of ethinyl estradiol)
 - Intrauterine hormone-releasing system (IUS) with a failure rate of < 1% per year
 - Oral contraceptives (either combined or progesterone only)
 - Injectable progesterone
 - Implants of levonorgestrel
 - Transdermal contraceptive patch
 - Contraceptive vaginal ring

Female subjects must also refrain from egg donation and in vitro fertilization during treatment and until at least 30 days after the end of relevant systemic exposure.

3) Contraception Requirements for Male Subjects

During the study, male subjects with female partners of childbearing potential should use condoms when engaging in intercourse of reproductive potential.

4) Unacceptable Birth Control Methods

Birth control methods that are unacceptable include periodic abstinence (e.g., calendar, ovulation, symptothermal, post-ovulation methods), withdrawal (coitus interruptus), spermicides only, and lactational amenorrhea method (LAM). Female condom and male condom should not be used together.

5) Procedures to be Followed in the Event of Pregnancy

Subjects will be instructed to notify the investigator if they become pregnant at any time during the study, or if they become pregnant within 30 days of last study drug dose. Subjects who become pregnant or who suspect that they are pregnant during the study must report the information to the investigator and discontinue study drug immediately. Instructions for reporting pregnancy, and pregnancy outcome are outlined in Section [7.6.2.1](#).

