- 8) Estimated glomerular filtration rate ≥ 30 mL/min according to the Cockcroft-Gault formula for creatinine clearance (eGFR_{CG}) {[Cockcroft et al 1976](#)}:

Male:
$$\frac{(140 - \text{age in years}) \times (\text{wt in kg})}{72 \times (\text{serum creatinine in mg/dL})} = \text{CL}_{\text{cr}} \text{ (mL/min)}$$

Female:
$$\frac{(140 - \text{age in years}) \times (\text{wt in kg}) \times 0.85}{72 \times (\text{serum creatinine in mg/dL})} = \text{CL}_{\text{cr}} \text{ (mL/min)}$$
- 9) Hepatic transaminases (AST and ALT) $\leq 5 \times$ upper limit of normal (ULN)
- 10) Total bilirubin ≤ 1.5 mg/dL, **and** normal direct bilirubin (subjects with documented Gilbert’s syndrome or with atazanavir-associated hyperbilirubinemia may have total bilirubin up to $5 \times$ ULN as long as direct bilirubin is normal)
- 11) Adequate hematologic function (absolute neutrophil count $\geq 1,000/\text{mm}^3$; platelets $\geq 50,000/\text{mm}^3$; hemoglobin ≥ 8.5 g/dL)
- 12) A female subject is eligible to enter the study if it is confirmed that she is:
 - a) Not pregnant confirmed by a negative serum pregnancy test, which is required for female subjects (unless permanently sterile or greater than two years post-menopausal)
 - b) Of non-childbearing potential (e.g., women who have had a hysterectomy, have had both ovaries removed or medically documented ovarian failure, or are postmenopausal women > 54 years of age with cessation (for ≥ 12 months) of previously occurring menses)
 - c) Female subjects who have stopped menstruating for ≥ 12 months but do not have documentation of ovarian hormonal failure must have a serum follicle stimulating hormone (FSH) level at screening within the post-menopausal range based on the Central Laboratory Reference range.

- d) Of childbearing potential and agrees to utilize the protocol specified method of contraception or be non-heterosexually active or practice sexual abstinence from screening throughout the duration of study treatment and for 30 days following discontinuation of study drugs (as defined in [Appendix 5](#))
 - e) Female subjects who utilize hormonal contraceptive as one of their birth control methods must have used the same method for at least three months prior to study dosing.

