5.4. Prior and Concomitant Medications

- Subjects receiving hormonal contraceptives should consider additional methods of contraception as concentrations of ethinyl estradiol may decrease and progesterin level may increase on co-administration with study drug.
- The use of medications for the treatment of HIV, other than study drug, is prohibited.
- Subjects receiving concomitant medications that are highly dependent on CYP3A for clearance and for which elevated plasma concentrations are associated with serious adverse events should consider alternative concomitant medications.
- During the study, subjects may not receive any of the following concomitant medications:
 - Competitors of renal excretion (e.g., probenecid; high-dose non-steroidal anti-inflammatory drugs)
 - Known nephrotoxic drugs (e.g., aminoglycosides, amphotericin B, vancomycin, cidofovir, foscarnet, cisplatin and pentamidine)
- Medications listed in the following table and use of herbal/natural supplements are excluded or should be used with caution while subjects are participating in the study. Any concomitant medication requiring adjustment or discontinuation due to renal impairment or a change in renal function on study should be managed per that drug's prescribing information.

Table 5-1. Prior and Concomitant Medications

Drug Class	Agents Disallowed	Use Discouraged and To Be Used With Caution
Acid Reducing Agents Antacids		Concentration of study drug may decrease with antacids. Subjects may not take antacids (e.g., Tums, Mylanta); the ulcer medication sucralfate (Carafate); or vitamin or mineral supplements that contain calcium, iron or zinc for a minimum of 2 hours before and 2 hours after any dose of study drug.
Alpha Adrenergic Receptor Antagonists	Alfuzosin	
Analgesics		Tramadol, Propoxyphene: Concentrations may increase with study drug(s); clinical monitoring is recommended.
Antiarrhythmics		Amiodarone, Flecainide, Quinidine, Propafenone, Systemic Lidocaine, Mexiletine, Disopyramide: Concentrations may increase with study drug(s) resulting in a potential for cardiac arrhythmias; clinical and ECG monitoring is recommended.
Calcium Channel Blockers	Bepidil	Felodipine, Nifedipine, Nicardipine, Verapamil, Diltiazem, Amlodipine: Concentrations may increase with study drug(s). Clinical and ECG monitoring of subjects is recommended.

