6.2. Pretreatment Assessments

6.2.1. Screening Visit

Subjects will be screened within 42 days before enrollment (Day 1) to determine eligibility for participation in the study. The following will be performed and documented at screening:

- Obtain written informed consent
- Obtain medical history, including history of HIV-1 disease-related events, cigarette smoking (current or previous smoker), diabetes, family cardiovascular history and prior medications within 30 days of the Screening Visit
- Complete physical examination (urogenital/anorectal exams will be performed at the discretion of the Investigator)
- Vital signs measurement (blood pressure, pulse, respiration rate, and temperature)
- Height and weight
- 12-lead ECG performed supine
- Urine collection for the following laboratory analyses:
 - Urinalysis and Urine chemistry

- Blood sample collection for the following laboratory analyses:
 - Serum pregnancy test (females of childbearing potential only). If the test is positive, the subject will not be enrolled.
 - FSH test is required for female subjects (age > 54 years) who have stopped menstruating for > 12 months but do not have documentation of ovarian hormonal failure.
 - Chemistry profile: alkaline phosphatase, AST, ALT, total bilirubin, direct and indirect bilirubin, total protein, albumin, bicarbonate, BUN, calcium, chloride, creatinine, glucose, potassium and sodium
 - Estimated glomerular filtration rate according to the Cockcroft-Gault formula (eGFR_{CG}) {Cockcroft et al 1976}:
 - Male:
$$\frac{(140 - \text{age in years}) \times (\text{wt in kg})}{72 \times (\text{serum creatinine in mg/dL})} = \text{CL}_{\text{cr}} \text{ (mL/min)}$$
 - Female:
$$\frac{(140 - \text{age in years}) \times (\text{wt in kg}) \times 0.85}{72 \times (\text{serum creatinine in mg/dL})} = \text{CL}_{\text{cr}} \text{ (mL/min)}$$
 - Hematology profile: complete blood count (CBC) with differential and platelet count
 - CD4+ cell count
 - Plasma HIV-1 RNA
 - Hepatitis B virus surface antigen serology (HBsAg)
 - Hepatitis C virus (HCVAb) serology (reflex HCV RNA is performed in subjects with positive HCVAb serology)
 - Whole blood sample collection for proviral genotype analysis of archived resistance
- Review of concomitant medications
- Record any serious adverse events and all adverse events related to protocol mandated procedures occurring after signing of the consent form.

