6.3. Treatment Assessments

6.3.1. Treatment Visits (Weeks 4 – 48)

The following evaluations are to be completed at the end of Weeks 4, 8, 12, 16, 24, 36 and 48 unless otherwise specified.

All study visits are to be scheduled relative to the Day 1 visit date. Study visits are to be completed within ± 2 days of the protocol-specified visit date through Week 16 and completed within ± 6 days of the protocol-specified visit date through Week 36, unless otherwise specified. The visit window at Week 48 will be ± 6 weeks of the protocol-specified visit date, which coincides with the Week 48 statistical analysis window for HIV-1 RNA. For the purposes of scheduling the Week 48 visit, a ± 6 day window of the protocol-specified visit date should be used.

Regularly scheduled evaluations will be made on all subjects whether or not they continue to receive study drug.

Note: At the Week 16 visit, the only assessments to be completed are:

- Review of AEs and changes in concomitant medications
- Blood sample collection for the following laboratory analyses:
 - Plasma HIV-1 RNA
 - Plasma sample storage for safety and virology testing
- Document study drug dispensation and accountability for all study drug dispensed.
- Questionnaire: Subject is to read questionnaire by her/himself and write/mark answers directly onto questionnaire.
 - Visual Analog Scale (VAS)

For all other visits, please complete the following:

- Review of AEs and changes in concomitant medications
- Complete physical examination (**Weeks 24 and 48**) (urogenital/anorectal exams will be performed at the discretion of the Investigator)
- Symptom-directed physical examination as needed (**Weeks 4, 8, 12 and 36**)
- 12-lead ECG performed supine (**Week 48 only**)
- Vital signs (blood pressure, pulse, respiration rate, and temperature), including weight
- Urine collection for the following laboratory procedures:
 - Urinalysis and urine chemistry
 - Urine pregnancy test (females of childbearing potential only); positive urine pregnancy tests will be confirmed with a serum test. If the test is positive, the subject will be discontinued.
 - Urine sample storage for possible additional clinical testing
- Blood sample collection for the following laboratory analyses:

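### The protocol gives conflicting rules on hormonal contraception, pregnancy testing and FSH testing, partly between Appendix 5 and the body and partly within each

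*Protocol*

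**What the plan says.** **Hormonal contraception.** Appendix 5, item 2(b), says of women of childbearing potential: "They must also not rely on hormone-containing contraceptives as a form of birth control during the study". Further down, the same item offers as an acceptable option: "Consistent and correct use of one hormonal method and one barrier method", followed by a list of hormonal methods. Criterion 12e in Section 4.2 says: "Female subjects who utilize hormonal contraceptive as one of their birth control methods must have used the same method for at least three months". Criterion 12d takes its definition of acceptable contraception from Appendix 5.

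**Pregnancy testing.** Appendix 5, item 2(b), says "A serum pregnancy test will be performed at all study visits" and adds a test at the end of relevant exposure. Section 6.3.1 lists, for treatment visits, "Urine pregnancy test (females of childbearing potential only); positive urine pregnancy tests will be confirmed with a serum test". Appendix 2 has a serum test at Screening only. It has urine tests at Day 1, Weeks 4, 8, 12, 24, 36 and 48, and the early study drug discontinuation (ESDD) visit. Section 6.3.1 gives a closed list of Week 16 assessments, and pregnancy testing is not on it. The 30-Day Follow-Up list in Section 6.4.2 has no pregnancy test either.

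**FSH.** Section 6.2.1 says "FSH test is required for female subjects (age > 54 years", with the further conditions of more than 12 months without menses and no documented ovarian hormonal failure. Criterion 12c requires a post-menopausal FSH value after at least 12 months without menses, at any age, if ovarian failure is undocumented. Criterion 12b counts women over 54 with at least 12 months' amenorrhea as of non-childbearing potential without mentioning FSH. Appendix 5, item 1(a), does the same from age 54 and otherwise uses FSH for women of any age.

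**The concern.** These are instructions that sites carry out, not background text. The contraception rule is part of eligibility through criterion 12d. The FSH rule helps decide who counts as of childbearing potential, and so who must use contraception and be tested. The testing rule sets when a pregnancy on study drug would be picked up on schedule. If two passages give different answers for the same woman, sites can differ on whether she may enroll, how she is classified and when she is tested, and each site can point to protocol text in support. What is at stake is participant protection and consistent conduct, not the efficacy result.

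**Working it through.** There is no figure in the plan to reproduce. The check compares passages and counts scheduled tests.

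**1. Hormonal contraception.** Take a woman using an oral contraceptive plus a male condom. The restriction in Appendix 5 2(b), read literally, excludes this. The hormonal-plus-barrier option in the same item accepts it. Criterion 12e accepts it if the hormonal method has been stable for three months. Because 12d points to Appendix 5, the conflict inside the appendix leaves her eligibility undetermined.

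**2. Pregnancy testing.** A completer has 10 scheduled contacts: Screening, Day 1, Weeks 4, 8, 12, 16, 24, 36 and 48, and the 30-Day Follow-Up.

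| Source | Serum | Urine | Contacts tested |
|---|---|---|---|
| Section 6 and Appendix 2 | 1 (Screening) | 7 (Day 1; Weeks 4, 8, 12, 24, 36, 48) | 1 + 7 = 8 of 10 |
| Appendix 5, follow-up visit not counted as a study visit | 9 | 0 | 9 of 10 |
| Appendix 5, follow-up visit counted | 10 | 0 | 10 of 10 |

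The ESDD visit adds one urine test for women who stop early.

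On-drug intervals between scheduled tests, in weeks:
- Section 6 and Appendix 2: 4, 4, 4, 12, 12, 12. The longest is 12.
- Appendix 5: 4, 4, 4, 4, 8, 12, 12. The longest is 12.

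Omitting Week 16 turns one stretch of 4 + 8 weeks into a single interval of 12. A pregnancy that would first show at Week 16 is then picked up on schedule at Week 24, which is 24 − 16 = 8 weeks later. After Week 48 or ESDD the schedule has no test, whereas Appendix 5 asks for one at the end of exposure. The Week 16 list is closed, so a site cannot meet both texts at that visit.

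**3. FSH.** Three illustrative women, each with 14 months' amenorrhea, not sterile and with no documented ovarian failure:

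| Age | Section 6.2.1 | Criterion 12c | Criterion 12b | Appendix 5 |
|---|---|---|---|---|
| 50 | FSH not called for | FSH required | Not covered by the age route | Of childbearing potential unless FSH is in range |
| 54 | FSH not called for | FSH required | Not covered (needs over 54) | Postmenopausal without FSH |
| 56 | FSH required | FSH required | Non-childbearing without FSH | Postmenopausal without FSH |

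No row gives one answer across the four passages. The 56-year-old's case shows criteria 12b and 12c disagreeing with each other, so part of this conflict lies within the body.

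**The case against.** The strongest case on the other side is that most sites would manage. The detailed list in Appendix 5 shows what is accepted, and the restriction could be read as barring hormonal methods used alone. The words of the sentence do not say that, so the reading is strained and the defect stands. On FSH, measuring it wherever any passage calls for it would satisfy them all, and the sponsor confirms eligibility before enrollment (Section 5.1). That limits variation between sites but does not make the text consistent.

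A reader might also infer several stronger points that the documents do not support.

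- **That a pregnancy on study drug would be missed.** The schedule tests at every on-drug visit except Week 16, with serum confirmation of positives. Appendix 5 adds a serum test for a delayed period and asks women to report a pregnancy up to 30 days after the last dose; nothing in the body contradicts either. What stands is possible later detection between Weeks 12 and 24, and no scheduled test after Week 48 or ESDD.
- **That Appendix 5 requires a test at the 30-Day Follow-Up.** The synopsis names study visits from Day 1 to Week 48 and mentions the follow-up separately, and the end of exposure is not tied to that visit. Only Week 16 is unambiguous.
- **That the rules on stopping for pregnancy contradict each other.** The opening of Section 6.6 is permissive, but its pregnancy bullet refers to Appendix 5, and Section 6.3.1 makes discontinuation mandatory after a positive test. For a confirmed pregnancy, 6.3.1 and Appendix 5 agree. The remaining difference is wording and trigger: Appendix 5 also acts on a suspected pregnancy.
- **That the interaction statements conflict.** Section 5.4 says "concentrations of ethinyl estradiol may decrease", which concerns drug levels. Appendix 5 2(a) says "there is no reduction in the clinical efficacy of hormonal contraception or that the effect on hormonal contraception is insignificant", which concerns clinical effect. Both can be true.

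**Conclusion.** The concern holds on three points: the restriction on hormonal contraceptives against the hormonal-plus-barrier option and criterion 12e; serum tests at all study visits against a urine schedule with no Week 16 test; and the FSH age limit in Section 6.2.1 against 12b, 12c and Appendix 5. The first lies partly within Appendix 5, the second between the appendix and the body, and the third partly within the body. Both texts cannot be met at Week 16 or, read literally, on hormonal methods. It would be wrong to say that of every item.

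The measurable difference is 8 tested contacts against 9 or 10, a different sample type at 7 of them, and up to 8 weeks' delay in scheduled detection between Weeks 12 and 24. This assumes visits at their nominal weeks and a woman who completes the study. The documents do not give the number of women of childbearing potential, so no count of affected participants is possible. No efficacy estimate is affected.

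**What to change.** Reconcile criteria 12b to 12e, Sections 6.2.1, 6.3.1 and 6.4.2, Appendix 2 and Appendix 5 so that each of the following has one rule, stated once and cross-referenced elsewhere:
- whether and how hormonal methods may be used;
- the sample type and timing of pregnancy tests, with Week 16 and the period after Week 48 or ESDD addressed explicitly;
- who has FSH measured, using the same age boundary and duration of amenorrhea throughout.

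Also align the wording of Section 6.6 on pregnancy with Section 6.3.1 and Appendix 5, and state whether the trigger is a confirmed or a suspected pregnancy. The copied schedule in SAP Section 1.2 and SAP Appendix 1 should follow whatever is decided. Which rule applies in each case is for the sponsor's medical team.

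The cost is wording in an amendment or a site letter, with no change to the sample size or analyses. If enrollment and follow-up have already ended, the study report should state which rules sites applied.
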